ENDPOINTS:	Primary Endpoint: Recruitment rates measured at 6 and 12 months and screen failures assessed by the detailed screen failure form at the time patients are approached for enrollment to ascertain specific reasons why patients may choose not to enroll Secondary Endpoints: 1. Laboratory (CBC, CMP, INR)/clinical toxicities measured using CTCAE version 5.0 2. Change in % radiotracer extraction from baseline, on functional HIDA scan, 3 months after treatment 3. Change in FACT-G and COST FACIT from baseline at 1, 3, and 6 months 4. ORR at 6 months after completion of treatment using mRECIST on multiphase CT or MR.
STUDY POPULATION:	20 (up to 10 enrolled per arm) male or female patients with small (\leq 3 cm) solitary hepatocellular carcinoma with relatively preserved liver function (CPS \leq 7)
PHASE:	N/A
DESCRIPTION OF STUDY INTERVENTION:	The SBRT arm of the trial will involve standard SBRT delivered over 3-5 fractions as tolerated with dose/total therapy adjusted as needed for safety. The RS arm of the trial will involve a planning arteriogram followed by selective transarterial delivery of Yttrium-90 into the segmental (≤2) artery supplying the tumor. Administered activity will be an amount prescribed to deliver a dose ≥200 Gy to the perfused tissue.
STUDY DURATION:	Estimated 12 months for accrual with another 24 months needed to complete secondary endpoints. 6 more months for data analysis. Total: 66 months
PARTICIPANT DURATION:	24 months from therapy completion. (approximately 26 months from randomization)

Protocol Version: 15DEC2021

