D Multi-phase contrast enhanced CT or MR of the abdomen. Baseline imaging should be obtained within 3 months of enrollment

E To be performed in patients receiving SBRT only prior to treatment

F To be performed in patients receiving RS only prior to treatment

G Required only in women of child bearing potential

H Adverse events will be reviewed and collected from the time of informed consent until 30 days after the 6 month visit. See section 12.4 for details

I SBRT arm only: Patients will be seen at least once per week by a clinician to grade toxicities during treatment, with on-treatment labs (CBC, CMP, INR) each week.

Protocol Version: 15DEC2021

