4.2 Secondary Objectives (SO)/ Secondary Endpoints (SE)

- SO: To compare the proportion of patients with toxicities (≥ grade 4) using CTCAE version 5.0 between RS and SBRT for patients with small (≤3 cm) solitary hepatocellular carcinoma (HCC). Only those toxicities at least possibly related to treatment will be considered.
 - **SE:** Laboratory (CBC, CMP, INR)/clinical toxicities measured using CTCAE version 5.0 up to 6 months post treatment.
- 2. **SO**: To compare the mean change in hepatobiliary function, as measured 3 months after treatment using a functional HIDA scan, between RS and SBRT for patients with small (≤3 cm) solitary hepatocellular carcinoma (HCC). SE: Change in % radiotracer extraction from baseline, on functional HIDA scan, 3 months after treatment
- 3. **SO:** To compare the mean change in patient-reported outcomes (PROs) from baseline, at 1, 3 and 6 months, between RS and SBRT, for patients with small (≤3 cm) solitary hepatocellular carcinoma (HCC), using FACT -G and COST FACIT questionnaires. **SE:** Change in FACT-G and COST FACIT from baseline at 1, 3 and 6 months
- 4. SO: To compare the disease-free survival (DFS) rates of RS and SBRT at 2 years using mRECIST on CT or MR for patients with small (≤3 cm) solitary hepatocellular carcinoma (HCC).SE: DFS at 2 years after treatment completion as measured with mRECIST on CT or MR
- 5. **SO:** To compare time-to-secondary treatment (TTST) between RS and SBRT for patients with small (≤3 cm) solitary hepatocellular carcinoma (HCC) up to 2 years after initial treatment. SE: TTST for target tumor up to 2 years following treatment.

6. **SO:** To measure the objective response rate (ORR) of radiation segmentectomy (RS) and stereotactic body radiation therapy (SBRT) as measured at 6 months using mRECIST (appendix IV) for patients with small (≤3 cm) solitary hepatocellular carcinoma (HCC) to better allow for an appropriately powered trial evaluating the efficacy of these treatments. **SE:** ORR at 6 months after completion of treatment using mRECIST on multiphase CT or MR.

Table 1: Justification for Endpoints

	OBJECTIVES	ENDPOINTS	JUSTIFCATION FOR ENDPOINTS		
Pri	mary				

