7.0 STUDY INTERVENTION

7.1 Study Interventions

There are two comparative intervention arms, both of which are currently standard-of-care.

7.1.1 Selective transarterial radioembolization (Radiation Segmentectomy (RS)):

This therapy arm involves two separate steps, a planning/mapping arteriogram and a therapy delivery. The planning arteriogram will be performed to confirm arterial anatomy is acceptable for RS (\leq 2 segment delivery) and that lung shunting is not too high to preclude treatment with RS. Once confirmed, patients will return for RS (within 45 days of mapping). Dose will be calculated based off the desired treatment volume using pre-treatment cross-sectional imaging. The desired segmental dose will be calculated to be \geq 200Gy. RS will be performed by one of three separate interventional radiologists with experience in radioembolization. Actual administered activity and location of dose administration will be recorded.

7.1.2 Stereotactic Body Radiation Therapy (SBRT):

SBRT will be delivered with linear accelerator-based photon beams with either fixed angle non-coplanar fields or dynamic arcs. For treatment planning, CT simulation with triple phase IV contrast would be performed in the treatment position (supine, arms up). Tumor motion management would be assessed with 4D CT through the breathing cycle. Abdominal compression or breath-hold may be used at physician discretion for diaphragmatic excursion of 1cm or more. Available pre-treatment diagnostic imaging will be fused with the planning CT by deformable registration to assist in target and normal tissue delineation. An internal target volume (ITV) will be generated to account for tumor movement during breathing cycle. Finally, a planning target volume (PTV) will be an expansion of 3-5mm from the ITV. For Child Pugh A patients, prescription dose will either be 5000cGy in 5 fractions delivered every other day or 4800cGy in 3 fractions delivered twice weekly. For Child Pugh B patients, prescription dose of 4000cGy in 5 fractions delivered every other day. Inverse planning will be used. 95% of the PTV or more will receive at least 100% of the prescription dose. Normal tissue dose constraints for each dose level will be respected with acceptable deviations permitted as outlined in appendix VII. Patients will be seen at least once per week by a clinician to grade toxicities, with on- treatment labs (CBC, CMP, INR) each week.

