8.0 STUDY EFFICACY AND SAFETY ASSESSMENTS

8.1 Efficacy Assessments

Patients will initially be flagged as potential candidates for the trial following a local tumor board discussion that the location and overall clinical picture would allow for either treatment as a viable option. Once tumor board agreement has been obtained, patients will be scheduled for a multi- disciplinary clinic visit where they will have a complete clinic visit with interventional radiology and radiation oncology back-

to-back. If after these visits patients fulfill inclusion/exclusion criteria, they will immediately thereafter be approached by a research coordinator and enrollment will be attempted.

If patients decline participation, a detailed screen fail form will be filled out to try and best ascertain reasons for declined participation. If the patient agrees to participate, they will be enrolled and randomized (as described above) at that time.

A virtual/telehealth provision will be permitted for all follow-up visits. Since the virtual visit does not allow for effective physical exam of all body systems and vitals are unable to be obtained virtually, these elements will not be required during virtual visits. Labs will be obtained, however, as well as required imaging. If questionnaires are required during a virtual/telehealth visit, they may be administered via REDCap survey.

Baseline: Labs, medical history/physical exam and PROs questionnaires will be obtained during the initial clinic visit prior to randomization. Subjects will be required to have an MRI or CT of the abdomen within 3 months of enrollment.

Pre-Treatment: Patients will return for functional hepatobiliary scan and treatment planning procedures prior to treatment (≤ 30 days from enrollment)

Treatment: Patients will undergo treatment as described above in Section 7.1.

Follow Up Visits:

One month (± 15 days) after treatment completion patients will return for a clinic visit with labs (CBC, CMP, INR, AFP (if elevated at baseline)), physical exam, and PROs using FACT-G and COSTFACIT.

Three months after treatment completion (± 30 days) patients will return for a clinic visit with labs (CBC, CMP, INR, AFP (if elevated at baseline)), physical exam, and PROs using FACT-G and COST FACIT. Patients will also undergo multi-phase contrast enhanced CT or MR of the abdomen and functional hepatobiliary scan.

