9.1 Study Intervention Not or Incompletely Performed

Study intervention arms both include a single treatment of the tumor, rather than an ongoing treatment. There is essentially one foreseeable area for necessary discontinuance in each arm.

Patients in the RS arm could potentially be found to have arterial anatomy precluding RS (3 or more segmental arteries supplying tumor or high lung shunt). While this is felt unlikely, it would preclude them from RS and they will be unanalyzable and removed from study to receive off-protocol treatment.

Patients in the SBRT arm will be monitored weekly for toxicities while on-treatment. While it is unexpected for patients to demonstrate toxicities that would preclude completion of the therapy cycle, if this were to occur, patients would be evaluated in the SBRT treatment arm, but designated to have had incomplete treatment.

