10.4 Populations for Analyses

The study will be performed as a modified Intention-to-treat analysis. Patients who were randomized to the radiation segmentectomy arm, but were later found to be to ineligible for RS based on the planning arteriogram findings, will be considered unanalyzable as they will have not received any protocol therapy and will proceed to other standard of care therapy. If this were to occur, a replacement patient will be added into the RS arm to help ensure a total of 10 patients in each arm.

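### Toxicity comparison: harm from the RS-only mapping arteriogram is lost for patients who fail mapping, and whether it counts for the rest is undefined

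*Combined protocol and SAP*

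**What the plan says.** Section 4.2 item 1 sets the comparison of grade 4 or higher toxicity as a secondary objective and restricts it: "Only those toxicities at least possibly related to treatment will be considered." The endpoint is laboratory and "clinical toxicities measured using CTCAE version 5.0 up to 6 months post treatment", which gives the end of the window but not its start. Treatment is not defined.

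The documents place the RS mapping arteriogram in two ways:

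- **Before treatment.** The Schedule of Events (1.3) lists it in the pre-treatment column, apart from administration of the study intervention. Footnote F reads "To be performed in patients receiving RS only prior to treatment". Section 8.1 says "Patients will return for functional hepatobiliary scan and treatment planning procedures prior to treatment".
- **Part of the RS intervention.** Section 7.1.1 says "This therapy arm involves two separate steps, a planning/mapping arteriogram and a therapy delivery". The synopsis, where it describes the intervention, says "The RS arm of the trial will involve a planning arteriogram followed by selective transarterial delivery of Yttrium-90".

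If arterial anatomy or lung shunt rules out RS, 9.1 says "it would preclude them from RS and they will be unanalyzable and removed from study to receive off-protocol treatment". Section 10.4 says such patients "will be considered unanalyzable as they will have not received any protocol therapy" and adds a replacement to the RS arm. By contrast, 9.1 keeps an SBRT patient who cannot finish the course in the SBRT arm, marked as incompletely treated.

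Adverse events are recorded from consent whatever their attribution (13.4), and their review is marked at the pre-treatment visit (1.3). Procedures are among the attribution categories for serious events (14.5). The relatedness filter appears only in 4.2. The synopsis, 10.2.2 and 10.5.3 refer to any toxicities and state no such condition.

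**The concern.** Each arm has a planning step, but the two differ in kind: an arterial procedure in RS, a contrast CT simulation in SBRT. A patient assigned to RS has to undergo mapping, so any harm it causes belongs to the comparison of the two strategies. If such harm is left out, the RS toxicity rate is too low, and SBRT has no arterial planning step to offset it.

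There are two routes to that loss. One is a stated rule: mapping failures leave the analysis set. The other is a gap: for patients who proceed to Y-90, the assessor decides whether a mapping event relates to treatment. The clinical investigator assigns attribution (13.1.3). Section 7.2 says overall blinding is not feasible and blinds only the radiology reading of response and DFS. A relatedness filter applied without blinding should not rest on an undefined word.

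**Working it through.** **Figure to reproduce.** None. The plan gives no expected toxicity rate, effect size, alpha or power, and 10.3 asserts the sample size of 20. The main check is therefore to trace patients through the rules.

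**Step 1. What happens to a grade 4 or higher event.**

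| Patient and event | Recorded (13.4) | In the analysis set | Counted under 4.2 |
|---|---|---|---|
| RS, event at mapping, then fails mapping | Yes | No (9.1, 10.4) | No, however treatment is read |
| RS, event at mapping, then receives Y-90 | Yes | Yes | No if treatment means delivery (1.3, 8.1); yes if it includes mapping (7.1.1, synopsis) |
| RS, event at Y-90 delivery | Yes | Yes | Yes, if at least possibly related |
| SBRT, event at CT simulation, then receives SBRT | Yes | Yes | Same ambiguity, but not an arterial procedure |
| SBRT, event during a course that is not completed | Yes | Yes (9.1) | Yes, if at least possibly related |

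The first row follows from the text. The second depends on which passages the assessor follows.

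**Step 2. Size of one event.** Inputs: 10 patients per arm (10.3); Fisher's exact test and 95% intervals (10.5.3); 0/10 events in SBRT, assumed for illustration. Intervals are Clopper-Pearson.

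- Event not counted: RS 0/10 = 0% (0 to 30.8%).
- Event counted: RS 1/10 = 10% (0.3 to 44.5%), a shift of 10 percentage points. With one event among 20 patients, each arm is equally likely to hold it, so the two-sided p = 0.5 + 0.5 = 1.00.
- Event in a mapping failure who is put back beside 10 treated RS patients: 1/11 = 9.1% (0.2 to 41.3%), p = 1.00.
- Mapping failure without an event put back, with one event elsewhere in RS: from 1/10 = 10.0% to 1/11 = 9.1%, which is 0.9 points lower.

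**Step 3. Could the test change?** Against 0/10 in SBRT, Fisher p is 0.47 for 2/10, 0.21 for 3/10, 0.087 for 4/10 and 0.033 for 5/10. Taking 0.05 as an assumed threshold, one added event changes the result only if RS already has four events and SBRT none.

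**Step 4. How likely is such an event?** The documents give no rate q of grade 4 or higher harm per arteriogram, so q is an assumption. The chance of at least one event in 10 mapped patients is 1 − (1 − q)^10:

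| Assumed q | Chance of at least one event |
|---|---|
| 0.5% | 4.9% |
| 1% | 9.6% |
| 2% | 18.3% |
| 5% | 40.1% |

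**Step 5. How many mapping failures?** Section 9.0 expects 10% unanalysable accruals from all causes, which is 0.10 × 20 = 2 patients. Section 9.1 considers mapping failure unlikely.

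**The case against.** The best counter-argument is that pre-treatment is a label for timing, while the filter in 4.2 is causal and broad, since a possible relation is enough. Section 7.1.1 and the synopsis put the arteriogram inside the RS intervention, 13.1.3 attributes events to the intervention, and 14.5 lists procedures as an attribution category. Nothing tells an assessor to call a mapping injury unrelated. This stands for patients who go on to Y-90. A reader might infer from 10.4 that the plan classes the arteriogram as outside protocol therapy for everyone. It does not: that wording concerns only patients found ineligible at mapping.

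Second, Table 1 justifies the endpoint by harm to the surrounding liver, so access-site or vascular events might be thought outside its purpose. That explains how they could be set aside, but 4.2 covers clinical as well as laboratory toxicity, and 10.2.2 covers any toxicity of this grade.

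Third, the filter is absent from 10.2.2 and 10.5.3, so under the statistical section alone a mapping event in a treated patient is not filtered out. That is correct, and it adds a conflict to be reconciled.

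None of this reaches the mapping failures, who leave the analysis before attribution matters.

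**Conclusion.** The point holds in two parts. For mapping failures, the rules in 9.1 and 10.4 remove any arteriogram harm from the comparison, with no matching rule in SBRT. For patients who receive Y-90, such harm may or may not be counted, because treatment is undefined and the passages conflict.

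A lost mapping event favours RS. Dropping an event-free mapping failure works slightly the other way (10.0% instead of 9.1% in Step 2). The effect is on the estimate, about 10 percentage points per event at 10 per arm, and hardly on the Fisher result.

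Two stronger readings are not supported. A reader might infer that half of all catheter-related RS harm is lost, because there are two catheterisations. That assumes equal risk at each, which the documents do not support, and it counts events where the endpoint counts patients. A reader might also infer that a biased toxicity rate would feed the sizing of the full trial, but the estimate that the documents name for that purpose is ORR.

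This is a secondary endpoint in a 20-patient feasibility pilot, so the consequence is modest. The change is still worth making, because a pilot's harm estimates should cover both arms on the same terms.

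**What to change.** 1. In 4.2 item 1, define related toxicity as at least possibly related to any arm-specific study procedure, from randomisation to 6 months post treatment. Name the mapping arteriogram and CT simulation as well as Y-90 delivery and SBRT.
2. In 9.1 and 10.4, state that for the toxicity analysis every randomised patient who starts an arm-specific procedure, mapping failures included, stays in the numerator and denominator of the assigned arm. Mapping failures have no protocol treatment date, so say what closes their window.
3. Insert the same relatedness rule in 1.1, 10.2.2 and 10.5.3, which now have none.
4. Record on the adverse event form the step to which each event is attributed, so that delivery-only rates can be shown beside the whole-strategy rates.

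The cost is wording in six places and one form field. Events are already recorded from consent, and 13.4 already follows those related to study procedures to resolution, so no new visit or procedure is needed. The downside is that the RS toxicity rate may look slightly less favourable.

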5.0 STUDY POPULATION

5.1 Inclusion Criteria

In order to be eligible to participate in this study, an individual must meet all of the following criteria:

- 1. Ability to provide written informed consent and HIPAA authorization
- 2. Stated willingness to comply with all study procedures and availability for the duration of the study
- 3. Male or female, aged ≥ 18 years at time of informed consent
- 4. Solitary HCC (≤3 cm) diagnosed by imaging (LI-RADS 4-5) or histology
- 5. Childs-Pugh score ≤ 7
- 6. ECOG performance status 0-1
- 7. Tumor location/characteristics eligible for either SBRT or Y90 therapy as deemed by local tumor board
- 8. Adequate organ function defined as:
 - a. serum bilirubin < 4.0 mg/dL
 - b. albumin > 2 g/dL

5.2 Exclusion Criteria

An individual who meets any of the following criteria will be excluded from participation in this study:

- 1. Any prior locoregional therapy to the target tumor
- 2. Any prior radiation therapy to the liver
- 3. Pregnancy or lactation: Women of childbearing potential must have a negative pregnancy test within 14 days of protocol registration. Women are considered to have childbearing potential (regardless of sexual orientation, having undergone a tubal ligation, or remaining celibate by choice) unless they meet one of the following criteria:
 - i. Has undergone a hysterectomy or bilateral oophorectomy; or
 - ii. Has been naturally amenorrheic for at least 24 consecutive months
- 4. Known severe allergic reaction (anaphylaxis) to iodinated contrast
- 5. Coagulopathy (platelets < 50 K/mm³ and/or INR > 2) not correctable by transfusion
- 6. Macrovascular invasion or extrahepatic HCC

5.3 Strategies for Recruitment

The majority of patients will be initially evaluated through the local liver tumor board. Currently, 1-2 patients who fit criteria are presented most weeks. It is estimated that around 50-60 patients in a year's time would be eligible. These patients will be set up to come to a multi-disciplinary clinic where they will have back-to-back clinic visits with both Interventional Radiology and Radiation Oncology on the same day. After both clinic visits are performed, a research coordinator (or if not available, an investigator) will approach eligible subjects and explain the trial and attempt enrollment. Direct referrals to either clinic who are eligible will also be seen by both specialties, and approached for the study, although this group will likely be much smaller than those discussed in tumor board.

6.0 PATIENT REGISTRATION

Patients who appear to be eligible for this trial will undergo the Informed Consent Process and be screened for eligibility utilizing the eligibility criteria. Eligible patients who complete the Informed Consent Process will be registered in the OnCore® database and assigned a patient ID number. Regulatory files will be maintained by the Department of Radiology. Applicable regulatory documents must be completed and on file prior to registration of any patients.

7.0 STUDY INTERVENTION

7.1 Study Interventions

There are two comparative intervention arms, both of which are currently standard-of-care.

7.1.1 Selective transarterial radioembolization (Radiation Segmentectomy (RS)):

This therapy arm involves two separate steps, a planning/mapping arteriogram and a therapy delivery. The planning arteriogram will be performed to confirm arterial anatomy is acceptable for RS (\leq 2 segment delivery) and that lung shunting is not too high to preclude treatment with RS. Once confirmed, patients will return for RS (within 45 days of mapping). Dose will be calculated based off the desired treatment volume using pre-treatment cross-sectional imaging. The desired segmental dose will be calculated to be \geq 200Gy. RS will be performed by one of three separate interventional radiologists with experience in radioembolization. Actual administered activity and location of dose administration will be recorded.

7.1.2 Stereotactic Body Radiation Therapy (SBRT):

SBRT will be delivered with linear accelerator-based photon beams with either fixed angle non-coplanar fields or dynamic arcs. For treatment planning, CT simulation with triple phase IV contrast would be performed in the treatment position (supine, arms up). Tumor motion management would be assessed with 4D CT through the breathing cycle. Abdominal compression or breath-hold may be used at physician discretion for diaphragmatic excursion of 1cm or more. Available pre-treatment diagnostic imaging will be fused with the planning CT by deformable registration to assist in target and normal tissue delineation. An internal target volume (ITV) will be generated to account for tumor movement during breathing cycle. Finally, a planning target volume (PTV) will be an expansion of 3-5mm from the ITV. For Child Pugh A patients, prescription dose will either be 5000cGy in 5 fractions delivered every other day or 4800cGy in 3 fractions delivered twice weekly. For Child Pugh B patients, prescription dose of 4000cGy in 5 fractions delivered every other day. Inverse planning will be used. 95% of the PTV or more will receive at least 100% of the prescription dose. Normal tissue dose constraints for each dose level will be respected with acceptable deviations permitted as outlined in appendix VII. Patients will be seen at least once per week by a clinician to grade toxicities, with on- treatment labs (CBC, CMP, INR) each week.

